10.5 Other Required Reporting

10.51 Unanticipated Problems Involving Risks to Subjects or Others (UPIRTSOS) in general, include any incident, experience, or outcome that meets **all** of the following criteria:

1. Unexpected (in terms of nature, severity, or frequency) given (a) the research procedures that are described in the protocol-related documents, such as the IRB-approved research protocol and informed consent document; and (b) the characteristics of the subject population being studied;
2. Related or possibly related to participation in the research (in this guidance document, possibly related means there is a reasonable possibility that the incident, experience, or outcome may have been caused by the procedures involved in the research); and
3. Suggests that the research places subjects or others at a greater risk of harm (including physical, psychological, economic, or social harm) than was previously known or recognized.

Some unanticipated problems involve social or economic harm instead of the physical or psychological harm associated with adverse events. In other cases, unanticipated problems place subjects or others at increased *risk* of harm, but no harm occurs.

Note: If there is no language in the protocol indicating that pregnancy is not considered an adverse experience for this trial, and if the consent form does not indicate that subjects should not get pregnant/impregnate others, then any pregnancy in a subject/patient or a male patient's partner (spontaneously reported) which occurs during the study or within 120 days of completing the study should be reported as a UPIRTSO.

If the event meets the criteria for an UPIRTSO, submit to your IRB as required by your institutional policies.

- 10.52 Pre-treatment symptoms/conditions to be graded at baseline and adverse events to be graded at each evaluation per the CTCAE v4.0 grading unless otherwise stated in the table below:

System Organ Class (SOC)	Adverse event/Symptoms	Baseline	Each evaluation
Infections and Infestations	Hepatitis viral*	X	X
Vascular Disorders	Thromboembolic Event	X	X
Blood and lymphatic system disorders	Febrile neutropenia	X	X
Gastrointestinal disorders	Upper gastrointestinal hemorrhage	X	X
Skin and subcutaneous tissue disorders	Rash Maculopapular	X	X

*See Drug Information Section 15.27.

- 10.53 **Case Report Forms** - Academic and Community Cancer Research United (ACCRU)

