Submit the following AEs not specified in Section 10.5 (paper or electronic, as applicable):

10.531 Grade 2 AEs deemed *possibly, probably, or definitely* related to the study treatment or procedure.

10.532 Grade 3 and 4 AEs regardless of attribution to the study treatment or procedure.

10.533 Grade 5 AEs (Deaths)

10.5331 Any death within 30 days of the patient's last study treatment or procedure regardless of attribution to the study treatment or procedure.

10.5332 Any death more than 30 days after the patient's last study treatment or procedure that is felt to be at least possibly treatment related must also be submitted as a Grade 5 AE, with a CTCAE type and attribution assigned.

- 10.54 **Late-Occurring Adverse Events** - Refer to the instructions in the Forms Packet (or electronic data entry screens, as applicable) regarding the submission of late occurring AEs following completion of the Active Monitoring Phase (i.e., compliance with Test Schedule in Section 4.0).

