16.23 Analysis Plans: All the relevant results pertaining to toxicity, MTD, response, timed endpoints and laboratory correlates will be examined in an exploratory and hypothesis-generating fashion. The small sample size and the heterogeneous patient population associated with phase I studies restricts the generalizability of the results. Any notable statistical result should only be viewed as preliminary evidence for further study in Phase II trials rather than a definitive finding in and of itself.

16.231 Adverse Events Profile

The number and severity of all adverse events (overall and by dose-level) will be tabulated and summarized in this patient population. The Grade 3+ adverse events will also be described and summarized in a similar fashion. This will provide an indication of the level of tolerance for this treatment combination in this patient group.

16.232 Toxicity Profile

The term toxicity is defined as adverse events that are classified as either possibly, probably, or definitely related to study treatment. Non-hematologic toxicities will be evaluated via the ordinal CTC standard toxicity grading. Hematologic toxicity measures of thrombocytopenia, neutropenia, and leukopenia will be assessed using continuous variables as the outcome measures (primarily nadir) as well as categorization via CTC standard toxicity grading.

Overall toxicity incidence as well as toxicity profiles by dose level and patient will be explored and summarized. Frequency distributions, graphical techniques and other descriptive measures will form the basis of these analyses.

16.233 Response Profile

A response is defined to be a CMR or PMR noted as the objective status after 2 cycles of treatment. All patients meeting the eligibility criteria who have signed a consent form and have begun treatment will be evaluable for response.

Responses will be summarized by simple descriptive summary statistics delineating complete and partial responses as well as no response and progressive disease in this patient population.

Phase II Portion

16.3 Statistical Design:

16.31 Decision Rule:

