16.421 **Overall proportion of patients (%) proceeding to stem cell transplant.** **Definition:** The percentage of patients proceeding to stem cell transplant will be estimated by the number of patients who proceed to transplant divided by the total number of evaluable patients. Exact

binomial 95% confidence intervals for the true success proportion will be calculated.

- 16.422 **Complete metabolic response (CMR) rate:** The CMR rate will be estimated by the number of patients with an objective status of CMR divided by the total number of evaluable patients. All evaluable patients will be used for this analysis. Exact binomial 95% confidence intervals for the true CMR rate will be calculated.
- 16.423 **Overall survival (OS):** Survival time is defined as the time from registration to death due to any cause. The distribution of survival time will be estimated using the method of Kaplan-Meier.
- 16.424 **Percentage of Adverse Events (%) categorized based on severity using CTCAE system/organ/class criteria 4.0.** Definition: All eligible patients that have initiated treatment will be considered evaluable for assessing adverse event rate(s). The maximum grade for each type of adverse event will be recorded for each patient, and frequency tables will be reviewed to determine patterns. Additionally, the relationship of the adverse event(s) to the study treatment will be taken into consideration. The frequency and percentage of patients experiencing a particular grade/severity of adverse event would be aggregated and combined data reported.
- 16.43 Correlative Analyses:
- 16.431 **Association of histologic subtype as assessed by pathology and its association with the primary endpoint of the study.** Definition: Histologic subtype (GCB vs.ABC vs. unclassified) from tumor tissue at the start of the study will be evaluated by 2 methods: Hans algorithm by IHC and gene expression profiling using nanostring technology. For each method, the relationship between overall response (responder vs. non-responder) CR rate and subtype will be evaluated using Chi-square tests (or Fisher's exact test if the data in the contingency table is sparse).
- 16.432 **Association of SUV reduction (%) noted on interim PET/CT scan with the primary endpoint of the study.** Definition: This will be evaluated by calculating the percentage (%) SUV reduction noted on interim PET/CT scan and correlated with the overall response (responder vs. non-responder) by using a two sample t-test .

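### Sections 16.231 and 16.424 promise adverse event tables below grade 3, but the case report forms collect only part of the grade 1–2 events, so low-grade rates for unlisted terms will be understated

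*Combined protocol and SAP*

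**What the plan says.** **Analysis.** Section 16.231, for phase I, states: "The number and severity of all adverse events (overall and by dose-level) will be tabulated and summarized in this patient population". A further table is then promised for events of grade 3 or higher. Section 16.424, the phase II secondary endpoint that serves goal 2.23, states: "The maximum grade for each type of adverse event will be recorded for each patient, and frequency tables will be reviewed to determine patterns". It goes on to report how many patients, and what percentage, have each grade. It says that relationship to treatment will be considered, but not how. Under Section 16.5 the secondary endpoints are reported to the public registry.

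**Collection.** Section 10.52 lists five terms (viral hepatitis, thromboembolic event, febrile neutropenia, upper gastrointestinal hemorrhage, maculopapular rash) under this instruction: "Pre-treatment symptoms/conditions to be graded at baseline and adverse events to be graded at each evaluation per the CTCAE v4.0 grading". For other terms, Section 10.53 names what is to be submitted:

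- at the lowest grade listed (10.531), only this: "Grade 2 AEs deemed *possibly, probably, or definitely* related to the study treatment or procedure"
- at grades 3 and 4 (10.532), every event, whatever the attribution
- deaths (10.533): those within 30 days of the last treatment whatever the cause, and later ones only if at least possibly related.

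**Two further routes.** Section 10.41 requires an expedited report of a serious grade 1–2 event with hospitalization of 24 hours or more, and Section 10.0(g) sends every expedited event to routine reporting too. Section 16.232 grades phase I thrombocytopenia, neutropenia and leukopenia from values, mainly the nadir.

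**The concern.** Because 16.231 adds grade 3+ as a further table, its main table is evidently meant to reach lower grades. For a term outside the five, however, a patient whose worst event is grade 1, or grade 2 judged unrelated, normally leaves no record and is counted as having had none. A reader of the table would take that as an observed absence.

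A maximum-grade table would also mix two rules without saying so: grade 2 filtered by an attribution judgement made in an open-label study, and grades 3–4 unfiltered. Section 15.17 names fatigue, diarrhea, constipation, nausea, peripheral neuropathy and muscle spasms among the very common events with lenalidomide (10% or more). None is a solicited term. Section 16.231 offers its tables as an indication of how well the combination is tolerated, so the gap bears on their stated purpose and, through 16.424, on percentages that will be published.

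**Working it through.** **Step 1: set collection beside analysis.**

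| Event | Reaches the routine data? | Source |
|---|---|---|
| Five listed terms, any grade or attribution | Yes | 10.52 |
| Unlisted, grade 3–4, any attribution | Yes | 10.532 |
| Death within 30 days, or later and related | Yes | 10.533 |
| Unlisted, grade 2, at least possibly related | Yes | 10.531 |
| Grade 1–2 with hospitalization of 24 hours or more | Yes | 10.41, 10.0(g) |
| Platelets, neutrophils, leukocytes (phase I) | Yes, from nadirs | 16.232 |
| Other unlisted grade 2, unrelated | No category | 10.53 |
| Other unlisted grade 1 | No category | 10.53 |

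The last two rows are the gap. No sentence in 16.231 or 16.424 limits the tables to the rows above them.

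**Step 2: direction.** An uncollected event can only remove a patient from a count. Grade 1 rates and all-cause grade 2 rates for unlisted non-hematologic terms can therefore only be understated.

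**Step 3: the plan's own figure.** The one stated figure that bears on capture is in 16.21: a toxicity with 25% incidence is seen in 6 patients with probability of at least 82%. Check: 1 − (1 − 0.25)^6 = 1 − 0.178 = 0.822. It reproduces, provided every case is recorded.

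**Step 4: illustration of scale.** Let c be the share of affected patients who have at least one collectable event. The documents do not give c, so the values below are assumptions. With a true any-grade incidence of 25%:

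- tabulated rate = 0.25 × c
- probability of at least one case in 6 patients = 1 − (1 − 0.25c)^6
- expected count among the 45 phase II patients = 45 × 0.25 × c

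| c | Tabulated rate | Seen in 6 patients | Expected of 45 |
|---|---|---|---|
| 1 | 25% | 0.822 | 11.25 |
| 0.75 | 18.75% | 0.712 | 8.44 |
| 0.50 | 12.5% | 0.551 | 5.63 |
| 0.25 | 6.25% | 0.321 | 2.81 |

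The third column needs care when set against 16.21. That statement concerns toxicities, which 16.232 defines as events at least possibly related. For those, only the grade 1 loss applies, so the 82% stands for related events of grade 2 or higher.

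**Step 5: what lies outside the gap.** In 7.62 the non-hematologic dose-limiting criterion starts at grade 3, and the hematologic ones are counts at day 29. The rules in 16.452 use dose-limiting toxicities or related non-hematologic events of grade 4 or higher. All of these are collected. The response endpoint does not use adverse event data.

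**The case against.** The best reply is that a tabulation of adverse events means those reported, and that most readers would understand it so. Section 16.23 declares the phase I results exploratory, and 16.424 says relationship to treatment will be considered. Section 18.1 also has a baseline adverse event form and a nadir/adverse event form at each evaluation, and their content is not in the documents; they may solicit more terms than 10.52.

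Part of this stands. The inclusive wording is in 16.231 only; 16.424 speaks of each type of event. The forms cannot be inspected. The consequence is confined to descriptive safety reporting. But neither section says that its tables cover collected events only, and an exploratory label does not make an incomplete count complete. As written, 10.53 is the rule for what is submitted.

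A reader might also infer more than the documents support:

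- *That every unrelated grade 2 event is lost.* The five listed terms, hospitalized events and phase I nadirs are captured.
- *That only the grade 3+ rows can be trusted.* Related grade 2 events are submitted, so tables of related events at grade 2 or higher are sound.
- *That comparisons between dose levels are biased in a known direction.* The same collection rule applies at every level. The comparison is incomplete at low grades, but no direction follows.

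**Conclusion.** The mismatch is real and unreconciled. If the plan is followed as written, grade 1 rates and all-cause grade 2 rates for unlisted non-hematologic terms will be understated in the tables of 16.231 and 16.424. The documents do not allow the amount to be estimated; the figures in the illustration rest wholly on the assumed share c. The conclusion assumes that 10.52–10.53 are the operative collection rule and that the unseen forms do not widen it.

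It would be a mistake to conclude that dose finding or stopping is undermined. Grade 3–4 rates whatever the attribution, related grade 2+ rates, the dose-limiting toxicity rule, the grade 4+ stopping rules and the response decision are not touched by this gap. It is a minor point, worth correcting because it determines which safety percentages are reported and how they will be read.

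**What to change.** In 16.231 and 16.424, define the tables by what is collected under 10.4 and 10.52–10.53:

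1. grade 3 or higher whatever the attribution, with late deaths limited as in 10.533;
2. grade 2 or higher, at least possibly related;
3. all grades only for the five terms of 10.52 and for hematologic nadirs;
4. grade 1–2 events with hospitalization of at least 24 hours, listed separately.

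Replace the inclusive wording of 16.231 accordingly, and report no all-grade total for other terms.

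The cost is revised text and table shells, with no new data. The drawback is that no all-grade incidence is reported for unlisted terms. If the study team wants that incidence, the alternative is to widen collection in 10.53 to all grades and attributions, at least in phase I, at the price of more data entry at the sites.

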Based on recent data and prior randomized controlled trials in the salvage setting for this patient population, the estimated overall response rate for two cycles of R-ICE based on similar salvage chemotherapy is around 45% (Gisselbrecht, Glass et al. 2010; Kewalramani, Zelenetz et al. 2004; Gyan, Damotte et al. 2013; Stewart, Duan et al. 2011; Thieblemont, Briere et al. 2011; Vacirca, Acs et al. 2014; Crump et al., 2014). For the addition of lenalidomide to be clinically meaningful, our hypothesis is that the addition of lenalidomide in the relapse setting would increase the overall response rate by approximately 20%.

The largest success proportion where the proposed treatment strategy would be considered ineffective in this population is 45%. The smallest success proportion that would warrant subsequent studies with the proposed treatment strategy in this patient population is 65%. The following one-stage design with an interim analysis based on a Simon optimum design (Simon 1989) uses 20 or 45 patients to test the null hypothesis that the true success proportion in a given patient population is at most 45%.

16.311 Interim Analysis Decision Rule: Enter 20 patients into the study. If 9 or fewer successes are observed in the first 20 evaluable patients, we will consider this regimen ineffective in this patient population and terminate this study. Otherwise, if the number of successes is at least 10, we will proceed with accrual.

16.312 Final Decision Rule: Enter an additional 25 patients into the study. If 24 or fewer successes are observed in the first 45 evaluable patients, we will consider this regimen ineffective in this patient population. If 25 or more successes are observed in the first 45 evaluable patients, we may recommend further testing of this regimen in subsequent studies in this population.

16.313 Over Accrual: If more than the target number of patients are accrued, the additional patients will not be used to evaluate the stopping rule or used in any decision making process. Analyses involving over accrued patients are discussed in Section 16.44.

16.314 NOTE: The trial will not be halted while the first 20 patients are evaluated for the interim analysis. However, if the accrual is especially rapid, we may temporarily suspend accrual to prevent missing important acute toxicity patterns.

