- 16.32 **Power and Significance Level:** Assuming that the number of responses is binomially distributed, with a significance level of 9%, the probability of declaring that the regimen warrants further studies (i.e., statistical power) and the probability of stopping after the interim analysis under various response proportions can be tabulated as a function of the true response proportion as shown in the table below.

If the true success proportion is...	0.45	0.50	0.55	0.60	0.65
Then the probability of declaring that the regimen is promising and warrants further study is...	0.090	0.249	0.491	0.735	0.900
And the probability of stopping after the interim analysis is...	0.591	0.412	0.249	0.128	0.053

- 16.33 **Other Considerations:** Toxicity, quality/duration of response, and patterns of treatment failure observed in this study, as well as scientific discoveries or changes in standard care will be taken into account in any decision to terminate the study.
- 16.4 **Analysis Plan:** The analysis for this trial will commence at planned time points (see 16.3) and at the time the patients have become evaluable for the primary endpoint. Such a decision will be made by the Statistician and Study Chair, in accord with CCS Standard Operating Procedures, availability of data for secondary endpoints (eg, laboratory correlates), and the level of data maturity. It is anticipated that the earliest date in which the results will be made available via manuscript, abstract, or presentation format is when the last patient has been followed for at least 2 months.

16.41 **Primary Endpoint:**

16.411 **Definition:** The primary endpoint of this trial is the overall response rate after two cycles of treatment. A response will be defined as a CMR or PMR noted as the objective status after two cycles of treatment. All patients meeting the eligibility criteria who have signed a consent form and have begun treatment will be evaluable for overall response, with the exception of patients who are determined to be a major treatment violation.

16.412 **Estimation:** The proportion of successes will be estimated by the number of successes divided by the total number of evaluable patients.

Confidence intervals for the true success proportion will be calculated according to the approach of Duffy and Santner (Duffy and Santner 1987).

16.42 **Secondary Endpoints:**

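### The futility stop is settled at the 11th confirmed non-responder, but the plan reads it only at 20 patients while accrual stays open; closing accrual at the 11th is a cheap improvement

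*Combined protocol and SAP*

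**What the plan says.** Section 16.31 sets the two reference rates: "The largest success proportion where the proposed treatment strategy would be considered ineffective in this population is 45" per cent, and "The smallest success proportion that would warrant subsequent studies with the proposed treatment strategy in this patient population is 65" per cent. The design is a single arm with one interim look, based on a Simon optimum design.

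- **Interim rule (16.311).** "If 9 or fewer successes are observed in the first 20 evaluable patients", the regimen is judged ineffective and the study ends. With 10 or more successes, accrual goes on.
- **Final rule (16.312).** "If 25 or more successes are observed in the first 45 evaluable patients", further testing may be recommended.
- **Accrual meanwhile (16.314).** "The trial will not be halted while the first 20 patients are evaluated for the interim analysis". The one exception is for especially rapid accrual, when "we may temporarily suspend accrual to prevent missing important acute toxicity patterns". That reason is toxicity, not futility.
- **Operating characteristics (16.32).** These are given "with a significance level of 9" per cent, with power 0.900 at a true rate of 65% and stopping probabilities of 0.591 at 45% and 0.053 at 65%.

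Two other sections bear on early termination. Section 16.33 lets patterns of treatment failure count in any decision to terminate. Section 16.451 has the principal investigator(s) and statistician review the study at least quarterly. Neither says what happens when the interim result is already determined.

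**The concern.** The interim rule is a count of successes among 20, so it has a mirror image: with 11 non-responders among those 20, no more than 9 successes are possible. From then on, the remaining assessments among the first 20 cannot change the decision. The plan nevertheless frames the decision at 20 observed patients and leaves accrual open until then. Patients can therefore start R2-ICE after the protocol's own rule can no longer be passed.

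What is at stake is patient exposure. The error rates and the sample size are not affected.

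**Working it through.** **Inputs from the documents.** Null rate 0.45 and target rate 0.65 (16.31); stop at 9 or fewer of 20 (16.311); promising at 25 or more of 45 (16.312); accrual of 4 to 5 evaluable patients per month (16.13); response read at cycle 2 day 21 with 21-day cycles, so about 42 days after start (11.1, 7.12); treatment to start within 14 days of registration (6.36).

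**Inputs assumed.** The documents give no time from registration to a known response. The range used is 1.4 months (42 days) to 2.3 months (14 days to start, plus 42 days, plus some delay). True rates of 30 and 35% are also assumptions.

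**Step 1. Reproduce the plan's table.** P(stop) = P(Bin(20, p) ≤ 9). P(promising) = Σ over x = 10 to 20 of P(X₁ = x) · P(Bin(25, p) ≥ 25 − x).

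| True rate | 0.45 | 0.50 | 0.55 | 0.60 | 0.65 |
|---|---|---|---|---|---|
| P(promising), stated | 0.090 | 0.249 | 0.491 | 0.735 | 0.900 |
| P(promising), recomputed | 0.0903 | 0.2490 | 0.4906 | 0.7352 | 0.9001 |
| P(stop), stated | 0.591 | 0.412 | 0.249 | 0.128 | 0.053 |
| P(stop), recomputed | 0.5914 | 0.4119 | 0.2493 | 0.1275 | 0.0532 |

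All entries agree to the precision printed.

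**Step 2. When is the stop settled?** Let T be the position of the 11th non-responder. P(T = t) = C(t − 1, 10) · (1 − p)¹¹ · p^(t − 11), for t = 11 to 20. At p = 0.45 these terms sum to 0.5914, which equals P(stop). The two rules are the same event, so curtailment changes no entry in the table.

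**Step 3. How many patients enter after T?** With steady accrual and equal lags, the readings of patient T and of patient 20 are delayed alike. The number starting between those readings is then 20 − T, whatever the accrual rate.

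At p = 0.45, the distribution of T given a stop is:

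| t | 11 | 12 | 13 | 14 | 15 | 16 | 17 | 18 | 19 | 20 |
|---|---|---|---|---|---|---|---|---|---|---|
| P(T = t given stop) | 0.002 | 0.012 | 0.032 | 0.061 | 0.097 | 0.131 | 0.157 | 0.171 | 0.173 | 0.165 |

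- Mean T is 17.3, so E[20 − T given stop] = 2.7.
- Over all trials at 45%: 0.5914 × 2.7 = 1.6.
- Nothing is saved when T = 20: 0.0974 / 0.5914 = 16.5% of stops. With irregular arrivals this share is higher, because a short gap may contain no new entry.
- The same sum gives 3.9 at a true rate of 35% and 4.6 at 30%. At 65% it gives 1.5 given a stop, so 0.0532 × 1.5 ≈ 0.1 per trial.

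**Step 4. Allow the lag to vary.** Simulation with random arrivals and a lag uniform on 1.4 to 2.3 months. Mean number enrolled at the stop, given a futility stop:

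| True rate | 4 per month: planned v curtailed | 5 per month: planned v curtailed |
|---|---|---|
| 0.45 | 27.8 v 24.8 | 29.8 v 26.7 |
| 0.35 | 27.8 v 23.6 | 29.8 v 25.5 |
| 0.30 | 27.8 v 22.8 | 29.8 v 24.7 |

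The saving at 45% is 3.0 to 3.1 patients given a stop, and accrual closes 0.6 to 0.75 months sooner. Over all trials that is 0.591 × 3.0 to 3.1, about 1.8.

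**Step 5. How often must the count be updated?** If the count is checked only every three months, a review falls between T and the 20th reading in 21 to 25% of stopped trials at 45%. The saving then drops to 0.6 to 0.7 patient.

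**The case against.** The strongest reply is that nothing here is wrong. A two-stage look at a fixed number of patients is ordinary practice, the table is correct, and the sections do not contradict each other. That stands: this is a suggestion.

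Four stronger readings are tempting, and the documents do not support them.

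- *That 3 to 5 patients will enter needlessly.* The figure is a mean among trials that stop for futility. The only ineffective rate the protocol states is 45%, which gives about 3. The upper end needs a true rate near 30%, which the protocol never posits and which lies below the 45% it assumes for R-ICE alone.
- *That the plan forbids an earlier stop.* It does not. Sections 16.33 and 16.451 leave room for discretion. But discretion is not a rule, and neither section ties closure to a settled interim result.
- *That any 11 non-responders fix the outcome.* Central pathology review is retrospective. Phase II patients found not to have DLBCL, or without enough tissue for subtype analysis, are to be replaced (3.12, 16.12), and major violations are not evaluable (16.411). A counted non-responder can therefore leave the first 20, so the 11 must be confirmed evaluable. The planned look shares this exposure, but a curtailed stop acts sooner, with fewer reviews complete.
- *That the evaluation lag removes the saving.* It makes some over-enrolment unavoidable, but it delays both readings by about the same amount, so the gap between them remains.

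Two practical objections also stand. The existing quarterly review is too slow to deliver the gain. And the confidence intervals in 16.412 use a method built for multistage tests, whereas a stop triggered by a failure count alters the sampling plan.

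**Conclusion.** The point holds as a cheap improvement to the interim rule and is of minor weight. Once 11 confirmed evaluable non-responders are seen among the first 20, the futility stop is settled, and the plan has no provision to close accrual then.

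At a true rate of 45%, the gain is about 3 patients on average if the trial stops (2.7 with equal lags, 3.0 to 3.1 with the assumed range). Across all trials it is about 1.6 to 1.8 per trial. With steady accrual and equal lags, about 16% of stops save nobody. At the target rate of 65% the gain is negligible. The figures rest on accrual of 4 to 5 per month, the assumed lag, and a count kept current as each response is reported. The significance level, power and stopping probabilities do not change, provided the 11 counted patients remain evaluable.

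**What to change.** Add to 16.311:

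> *Accrual closes as soon as 11 of the first 20 patients are confirmed evaluable non-responders; the statistician updates this count as each cycle 2 response assessment is reported. Patients already enrolled are evaluated per protocol and stay in the estimates.*

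Add a line to 16.412 saying how the confidence interval is formed if fewer than 20 patients are enrolled at the stop. The final rule in 16.312 and the table in 16.32 stay as they are.

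**Cost.** Response must be tracked as it is reported, with evaluability confirmed for the patients counted. The estimate is slightly less precise when fewer than 20 patients are enrolled at the stop. At 45% that is roughly 3 to 7% of futility stops with the assumed lag of 1.4 to 2.3 months, or about 8 to 14% if every response is known at 42 days and arrivals are irregular.
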